8.9.1 Randomization Assignment and Study Treatment

A study participant will be randomly assigned to treatment or control after determining he/she meets the study procedure eligibility criteria during the bronchoscopy procedure (see Section 11.2). If the study participant does not meet the study procedure eligibility criteria, he/she will not be randomly assigned to treatment nor receive any study-related treatment. If the study candidate is found to meet the study procedure eligibility criteria, then (s)he will be randomly assigned to study treatment during the bronchoscopy procedure.

Random assignment will be conducted using an allocation ratio of 2:1; two study participants will be randomized to the EBV Treatment arm for every one participant randomized to the Control arm. Random assignment will be conducted using a stratified permuted block design generated separately for each clinical site, with assignment stratified by anatomical site of the planned treatment (e.g. right lung or left lung). Mixed block sizes will be used. The goal of stratification will be to ensure a 2:1 randomization mix within each stratum.

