15.4.6 Continuing COPD exacerbations

In cases where a study participant has recurrent COPD exacerbations, valve removal may be considered.

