An interim data analysis designed to evaluate effectiveness for continuing crossover of control arm study participants at 1 year to EBV treatment will be performed when 74 (50% of the total 147) study participants have completed the 1 year follow-up. The interim analysis will be

reviewed by the DSMB and FDA. If crossover of control arm study participants is found to be justified by the interim analysis, then crossover of control arm study participants may be continued. If the DSMB recommends not continuing crossing control arm participants to EBV treatment, then those control arm patients who have not yet crossed over will exit from the study per protocol after the 1-year visit.

Long-Term Follow-up

Data will be collected annually through 5 years. Per the regulatory plan agreed to with FDA, 1 year of follow-up is required pre-approval and the remaining 4 years will be conducted post-approval. The 2-, 3-, 4-, and 5-year data will consist of FEV₁ and adverse events.

Definition of Study Success: The study will be a success if the difference between the EBV Treatment arm and Control arm for the percentage of study participants meeting the threshold of $\geq 15\%$ improved in FEV₁ differs significantly (two-sided test at $p \leq 0.05$) in favor of the treatment group at 1 year. This evaluation will be conducted at 1-year post-randomization.

Number of Study Participants: 183

Statistical Methods

I. Descriptive Statistics

Means, standard deviations, medians, and confidence intervals will be reported for all continuous variables. Dichotomous variables will be reported as percentages and the numerator and denominator will be reported and defined. The frequency of adverse events will be reported as percentage rates with computed 95% two-sided exact confidence intervals (upper and lower).

II. Analyses of the Patient Populations

These analyses are intended to determine the similarity of two treatment groups and similarity of patients from different study sites with respect to important demographic or other variables, either known or suspected to have an influence on the outcome variables. The absence of similarity for any variable will identify that variable as a potential covariate in subsequent analyses.

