Pulmonx Corporation

Clinical Investigational Plan #630-0012_H

Statistical Analysis Plan – Revised 26 October 2017 (supersedes Appendix 19 from CIP #630-0012_H)

Change History:

SAP Section	Change	Rationale
Study Design	Update the enrolled study participants to 190.	To reflect the number of study participants enrolled in the study.
Secondary Effectiveness Endpoints	Analyses of secondary endpoints were updated to limit the number of statistical comparisons. Now limited to Absolute Change in FEV1, 6MWD, and SGRQ score. The use of Hochberg method was specified to address multiplicity.	To control the family-wise Type I error for the secondary endpoints, analyses of secondary endpoints were limited.
Safety Endpoint	Deleted "of the EBV treatment arm".	To reflect that adverse events will be compared between treatment arms during the short-term and long-term periods.
Additional Measures	Additional measures were updated, specifically, Treatment Lobe Volume Reduction (TLVR) for the treatment arm only was moved from Secondary to Additional.	Moved to "Additional Measures" since this parameter indicates the mechanism of action and unable to compare to a Control group as no TLVR is expected without an intervention.
Statistical Methods – I	Confidence intervals were removed from adverse event reporting. In place of presenting confidence intervals, adverse event rates for those events occurring in at least 3% of subjects in either group will be compared using a Fisher's Exact test.	Making adverse event reporting consistent with typical way of presenting and analyzing adverse events.
Statistical Methods II (C)	Pseudo-sites clarified to be created from sites within the same country.	Clarification.
Statistical Methods III	Definitions of populations clarified.	Clarification.
Statistical Methods IV	Update to "three" secondary effectiveness variables in the text and in Table 3.	To reflect the modified secondary effectiveness endpoints.
Statistical Methods IV (B)	Update to analyses of secondary endpoints, including use of Hochberg method.	To control the family-wise Type I error for the secondary endpoints,

		analyses of secondary endpoints were limited.
Statistical Methods IV (C)	Update to analyses of additional effectiveness endpoints.	As a result of modifying the secondary effectiveness endpoints, additional measures were also updated.

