Study Design: This will be a multi-center, prospective, randomized, controlled study with EBV treatment statistically evaluated using Intent-to-Treat (ITT) analyses. A maximum of 183 ITT study participants, who meet study entry criteria, consisting of screening eligibility criteria, baseline eligibility criteria, and procedure eligibility criteria, were planned to be enrolled. A total of 190 study participants were enrolled. Safety and effectiveness of bronchoscopic lung volume reduction (BLVR) using the Pulmonx EBV will be evaluated at 1 year. An interim analysis designed to evaluate effectiveness for continuing crossover of control participants at 1 year to EBV treatment will be performed when 74 study participants have completed the 1-year follow-up. For study participants who have been treated with EBV, a secondary valve intervention such as valve removal, replacement, or adjustment may be considered during the study follow-up. Long-term data will be collected annually for EBV-treated study participants through 5 years. Per the regulatory plan agreed to with FDA, 1-year of follow-up is required pre-approval and the remaining 4 years of follow-up will be conducted post-approval.

Primary Effectiveness Endpoint

The percentage of study participants in the Endobronchial Valve (EBV) treatment arm who meet the threshold of \geq 15% improved forced expiratory volume in one second (FEV₁) as compared to the control arm at 1 year. Improved FEV₁ will be calculated by determining the percentage change for FEV₁ from baseline to 1-year post-procedure for individual study participants.

Secondary Effectiveness Endpoints

- 1) FEV₁: Difference between study arms in 'absolute change from baseline' for FEV1 at 1 year.
- 2) 6-Minute Walk Distance (6MWD): Difference between study arms in 'absolute change from baseline' for 6MWD at 1 year.
- 3) St. George's Respiratory Questionnaire: Difference between study arms in 'absolute change from baseline' for SGRQ score at 1 year.

Safety Endpoint

Evaluation of the short- and long-term adverse events profile during the treatment period, defined as the day of the study procedure until 45 days after the study procedure (short), and in the post-treatment period, defined as 46 days after the study procedure until the 1-year followup visit (long).

Additional Measures

- Treatment Lobe Volume Reduction (TLVR) for the treatment arm only
- Spirometry, including FEV₁, forced vital capacity (FVC) and the ratio of FEV₁/FVC

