inter-lobar fissures	percent complete	percentage of participants

V. Adjustment for Potential Confounders

The covariates shown in Table 6 may be potentially influential with respect to the effectiveness endpoints. If any of these covariates are found to be out of balance between the groups (at the two-sided 0.10 level), they will be included in a multivariate analysis, along with an indicator of treatment group, to evaluate their potential effect on the study conclusions. A multivariate logistic regression model will be used for primary and secondary endpoints.

Table 6. Covariates

	Baseline	Procedure
Gender	X	
Age	X	
Clinical Site	X	
6MWD	X	
Patient-reported health status measures (e.g. SGRQ)	X	
Body Mass Index	X	
BODE Index	X	
Medication Use	X	
Residual Volume (RV)	X	
RV % Predicted	X	
Total Lung Capacity (TLC)	X	
TLC % Predicted	X	
RV/TLC	X	
IC/TLC	X	
Vital Capacity	X	
Forced Vital Capacity (FVC)	X	
FVC % Predicted	X	
FEV ₁	X	
FEV ₁ % Predicted	X	
FEV ₁ / FVC	X	
Lobar Volume	Х	
Lobar Destruction Scores	Х	
Ipsilateral DS Heterogeneity	X	
Severity of emphysema (GOLD classification)	X	
Comorbidities	X	
Target Treatment Lobe		Х
Treatment Group		Х

VI. Secondary Valve Procedures

Secondary valve procedures will be evaluated by examining the proportion of patients who undergo valve removal, valve replacement, or valve adjustment, and describing the reasons they occurred. Data for these study participants will be contrasted to data for study participants who did not receive a secondary valve procedure.

VII. Safety Analyses

Evaluation of the short- and long-term adverse events profile during the treatment period, defined as the day of the study procedure until 45 days after the study procedure (short), and in the post-treatment period, defined as 46 days after the study procedure until the 1-year follow-up visit (long). For the Control arm, the date of study procedure will be considered the date of the bronchoscopy assessment. Safety analyses will be performed by examining the percentage of patients that experiences adverse events. The rates and 95% exact confidence intervals will be presented on an event and on a per-patient basis. The percentage of subjects reporting adverse events occurring in at least 3% of subjects in either treatment arm will be compared using a Fisher's Exact test.

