Adverse events will be categorized into clinically relevant groups (*e.g.:* stable pneumothorax with no intervention, pneumothorax resolved with chest tube insertion in less than 7 days,

prolonged air leak, etc.). Adverse events occurring in the treatment arm will be further categorized by severity and as device-related, procedure-related, or neither, and by those occurring during procedure hospitalization and those occurring post-discharge.

Rehospitalization rates will be reported by study arm on a Per-Patient (PPt) basis and on a Per-Event (PE) basis. In study participants who receive EBV treatment, adverse events will be evaluated by stratifying participants by use of conscious sedation and general anesthesia during the bronchoscopy procedure as well as evaluating number of valves received and sites EBV were placed.

VIII. Mortality

A Kaplan-Meier survival curve for each study arm will graphically display the time to death from the time of randomization and a log rank test will be used to compare Kaplan-Meier curves between study arms. A Cox proportional hazards model will be used to control for study site along with other significant co-variates as applicable.

IX. Patient Accountability and Missing Data

Every effort will be made to collect all data points in the study. The sponsor plans to minimize the amount of missing data by appropriate management of the prospective clinical trial, proper screening of study subjects, and training of participating investigators, monitors and study coordinators.

- The analysis for the primary endpoint will be performed by imputing missing data. Subject death prior to the 1-year visit date will be imputed as failure.
- For study participant FEV₁ data that is 'intermittent', missing outcomes will be imputed by linear interpolation using the FEV₁ value from the latest non-missing data point before the missed data point and the earliest non-missed data point after the missed data point.

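### The event-basis exact confidence interval for adverse events makes no allowance for repeat events within a patient and names no distribution or denominator (low severity)

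*SAP*

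**What the plan says.** The current SAP, Section VII, summarises adverse events mainly as the percentage of patients affected, then adds: "The rates and 95% exact confidence intervals will be presented on an event and on a per-patient basis". It does not name the distribution behind the word exact. Nor does it say whether the event rate is divided by patients, patient-time or all events, or how repeat events in one patient are handled. The same sentence stands in the superseded Appendix 19, Section VII.

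The between-arm comparison in the same section is a per-subject test: "The percentage of subjects reporting adverse events occurring in at least 3% of subjects in either treatment arm will be compared using a Fisher's Exact".

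The protocol foresees repeat events. Section 15.4.6 reads: "In cases where a study participant has recurrent COPD exacerbations, valve removal may be considered". SAP VII also separates the two ways of counting for another outcome: "Rehospitalization rates will be reported by study arm on a Per-Patient (PPt) basis and on a Per-Event (PE) basis". That sentence asks for no interval. It shows only that per-patient and per-event figures are treated as different quantities.

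The SAP change history, in the row for Statistical Methods I, says: "Confidence intervals were removed from adverse event reporting". Its row for Section VII says that Fisher's exact tests take their place.

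**The concern.** An exact interval is exact only under its model. The binomial model needs independent yes/no outcomes, one per unit. The Poisson model needs events that arise independently at a common rate. COPD exacerbations and similar respiratory events can recur in the same patient over a year, and patients differ in how prone they are to them. Such counts vary more between patients than either model allows, so the interval comes out too short.

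The safety endpoint is the adverse event profile over two periods. A nominal 95% interval with much lower coverage would overstate how well the frequent, recurrent events are known. Leaving the method unnamed also means that it may be chosen after the data have been seen.

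**Working it through.** The plan states no adverse event count, event rate or interval width, so there is no planned figure to reproduce.

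**Inputs from the documents**
- Enrolled: 190 (SAP, Study Design: "A total of 190 study participants were enrolled").
- Allocation: 2:1 (Protocol 8.9.1: "Random assignment will be conducted using an allocation ratio of 2:1").

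**Assumptions, because the documents give no figure**
- Valve arm size n: 190 × 2/3 = 126.7, taken as 127.
- Mean events per patient m: 0.05 to 1.2.
- Counts per patient: Poisson (no clustering), or gamma-Poisson with shape k = 1 or 0.5. The variance/mean ratio is 1 + m/k. At m = 0.6 this is 1, 1.6 and 2.2.

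**Intervals, for x events in n patients**
- Exact binomial (Clopper-Pearson): lower limit is the 2.5% point of Beta(x, n − x + 1), upper limit the 97.5% point of Beta(x + 1, n − x). It needs x ≤ n.
- Exact Poisson: lower limit is the 2.5% point of chi-square on 2x degrees of freedom, divided by 2n; upper limit is the 97.5% point on 2x + 2, divided by 2n.

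**Examples with n = 127**
- 100 events: binomial 70.6% to 85.5%; Poisson 0.641 to 0.958 per patient.
- 160 events: binomial does not exist (160 > 127); Poisson 1.072 to 1.471.
- For contrast, a valid per-patient interval: 25 of 127 patients = 19.7%, 13.2% to 27.7%.

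**Why the intervals are short.** Standard errors of the event rate at m = 0.6:
- implied by the binomial: √(0.6 × 0.4/127) = 0.043
- implied by the Poisson: √(0.6/127) = 0.069
- true value at k = 1: √(0.6 × 1.6/127) = 0.087
- true value at k = 0.5: √(0.6 × 2.2/127) = 0.102

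**Coverage of the nominal 95% interval.** The total count is Poisson with mean 127m, or negative binomial with size 127k and mean 127m. Coverage is the total probability of those counts whose interval contains m. For the binomial it is taken over the counts where the interval exists. Each entry gives Poisson counts / k = 1 / k = 0.5.

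| m | Binomial over patients | Exact Poisson |
|---|---|---|
| 0.05 | 97% / 97% / 97% | 97% / 97% / 97% |
| 0.1 | 95% / 94% / 93% | 97% / 96% / 95% |
| 0.3 | 91% / 87% / 82% | 96% / 92% / 89% |
| 0.6 | 81% / 70% / 63% | 95% / 89% / 82% |
| 1.2 | not computable in 98% / 92% / 87% of trials | 95% / 82% / 72% |

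**A third denominator.** If the interval is for a share of all events, it can always be computed. It still treats one patient's repeat events as independent, so the same objection applies.

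**After the fix.** An interval from the between-patient variance (mean ± 1.96 × SD/√n) was simulated with 5,000 runs per setting. At 0.6 events per patient it covered 94.7%, 94.3% and 92.2% at variance/mean ratios 1, 2 and 3. At 0.25 events and ratio 3 it covered 89.6%. The exact Poisson interval covered 77.1% there and the binomial 72.5%.

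**The case against.** The strongest reply is that the SAP never calls the event interval binomial. A reader might infer that it specifies an interval that cannot be computed, but the text does not support that. An exact Poisson interval fits the wording, always exists, and covers about 95% when events are independent at a common rate. The nearest support for a binomial reading is the reference to percentage rates with exact intervals in Section I of the superseded Appendix 19, and that sentence is not in the current Section I. This part of the reply stands.

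The Poisson reading still does not account for clustering. How far coverage falls depends on overdispersion, for which the documents give no figure. Some is plausible in patients who differ in severity, but its size is an assumption.

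A reader might also take the rehospitalization sentence as a second instance. It mentions no interval, so it is not one.

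Finally, the sentence in Section VII may be a leftover, because the change history says that adverse event intervals were replaced by Fisher tests. A difference between a change log and the current text is not an error in itself. It does make it sensible to ask first whether the intervals will be produced at all.

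**Conclusion.** The point holds in limited form. SAP VII asks for exact intervals on an event basis, repeat events are foreseen, and neither a binomial nor a Poisson exact interval allows for them.

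The shortfall matters for frequent, recurrent events. Under the assumptions of 127 patients and 0.6 events per patient, coverage is between 63% and 81% on the binomial reading. On the Poisson reading it is 82% to 89% with clustering and about 95% without. At 0.1 events per patient or fewer, coverage is about 93% to 97% on either reading.

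It would be tempting to conclude that the safety evaluation as a whole is unsound. The documents do not support that. The main safety summary is per patient, its exact intervals are valid, the Fisher tests count subjects, and study success rests on FEV₁ responders alone. Severity is low.

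**What to change.** In SAP VII, limit exact binomial intervals to the percentage of patients with an event. For event-based summaries, state the denominator (patients or patient-time), give the event count and the rate, and use an interval that allows for repeat events: negative binomial, Poisson with robust variance, or a bootstrap that resamples patients. Event counts without an interval would also be acceptable. The sponsor should confirm whether adverse event intervals are still planned, and align Section VII with the change history.

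The cost is one or two sentences and a standard procedure. Intervals for recurrent events become wider: in the simulation at 0.6 events per patient and a variance/mean ratio of 2, the average width was 0.38, against 0.28 for exact Poisson. A robust interval can still fall below 95% for sparse, highly clustered events, as the 89.6% above shows.

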15.0 SAFETY ELEMENTS

15.1 Adverse Events

Previous studies of emphysema patients who were followed longitudinally and treated using medical management [10,16,17], diagnostic or interventional bronchoscopy [448,49], or endobronchial valves [16,17] indicate that a moderate risk of adverse events may be anticipated during this study. Adverse events will be graded by defining their severity and relatedness to the study device.

It is anticipated that the rates for adverse events will be higher for the study treatment arm than control arm during the treatment period ('short', or day of the study procedure to 45 days) but that the rates for these occurrences will be similar for both study arms during the post-treatment period ('long', or 46 days to 1 year).

Adverse events that may be observed include:

- ❖ Cardiovascular events such as:
 - New onset cardiac arrhythmia
 - New diagnosis of congestive heart failure, which may be indicated by ≥ 1 -point increase in NYHA functional classification score
 - Acute myocardial infarct requiring medical care
 - New diagnosis transient ischemia attack (TIA) or stroke
 - New diagnosis deep vein thrombosis
 - Pulmonary embolism, which may be indicated by direct clinical evidence or V/Q evidence of segmental or larger perfusion defects

- ❖ COPD and Emphysema events such as:
 - COPD exacerbation requiring treatment with antibiotics and/or oral steroids
 - AECOPD requiring emergency room visit or hospitalization
 - Respiratory failure requiring re-intubation at any time during follow-up and/or invasive mechanical ventilation >24 hours after the bronchoscopy procedure
 - Pneumonia requiring treatment with antibiotics, indicated by consolidation on X-ray or CT scan and clinical characteristics of active infection (fever, leukocytosis, hypotension)

- ❖ Pulmonary / Thoracic events such as:
 - Hemoptysis requiring new evaluation or intervention
 - Pneumothorax indicated by clinical symptoms and/or X-ray
 - Pneumothorax requiring intervention
 - Empyema requiring new evaluation or intervention
 - Non-cardiac chest pain driving the study participant to seek medical care
 - Pleural effusion noted radiologically
 - Lung mass / cancer noted radiologically
 - Fractured rib noted radiologically
 - Laryngospasm driving the study participant to seek medical care
 - Dysphonia driving the study participant to seek medical care
 - Hypoxemia requiring increased or new oxygen use

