20.3.1 Sample Size Rationale

The results of two prospective studies were used to inform the sample size estimation. The Endobronchial Valve for Emphysema Palliation Trial ("VENT Pivotal Trial", IDE#G020230, NCT00129584) was a multi-center, prospective, randomized, controlled study conducted at sites in both the United States and Europe to assess the safety and effectiveness of using the Zephyr EBV device for palliating symptoms associated with severe heterogeneous emphysema. Four hundred ninety two (492) participants were enrolled into the study and randomized to Zephyr EBV Treatment or medical management (control) [16,17]. The Chartis Pulmonary Assessment System study is a recently completed prospective post-market study that was conducted in Germany, The Netherlands, and Sweden. The primary objective of the study was to quantify the accuracy of the Chartis System when used to identify targeted treatment lobes as having or not having inter-lobar CV in patients with emphysema who were to be treated using endobronchial valves (26). The results of both the VENT Study and the Chartis System study showed that treatment effect with the endobronchial valve is correlated with lack of inter-lobar CV [16,17,25].

Patients in the VENT Study and in the Chartis Study who were considered to have little or no inter-lobar CV contributed the information used for the sample size estimate. Patients who have little or no lobar CV in the targeted treatment lobe are expected to be good responders to endobronchial valve treatment. For the sample

size estimate, a 'responder' was considered to be a study participant who had $\geq 15\%$ improved FEV₁ after EBV treatment.

Based on the results of these studies, the responder rate in the EBV Study Treatment Group is expected to be approximately 35% at 1 year. The responder rate for the control group is not expected to exceed 10% at 1 year. Assuming a two-sided 0.05 alpha level, study power of 90%, and 2:1 allocation random assignment, a sample size of 147 will be adequate to test for superiority.

The study sample size will be increased to 183 in order to allow for 20% lost to follow-up and incomplete data. Each study site will be allowed to enroll a maximum of 25 study participants.

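### SAP VII compares adverse events between arms by Fisher's exact test but gives no between-arm risk difference or interval for it, so a non-significant result may be misread as similar safety

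*SAP*

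**What the plan says.** SAP section VII covers two periods: day 0 to day 45, and day 46 to the 1-year visit. It plans two things for adverse event incidence.

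- Description: "The rates and 95% exact confidence intervals will be presented on an event and on a per-patient basis".
- Comparison: the percentages of subjects with "adverse events occurring in at least 3% of subjects in either treatment arm will be compared" by Fisher's exact test. Section VII states no significance level for these tests.

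Neither SAP VII nor the protocol's safety sections specify a risk difference, a ratio, or an interval for a between-arm contrast in adverse events. Deaths are handled separately in SAP VIII by Kaplan-Meier curves, a log-rank test and a Cox model.

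The SAP change history shows that the safety endpoint was reworded so that events are compared between arms. Protocol section 15.1 anticipates higher rates with EBV in the first 45 days, but that "the rates for these occurrences will be similar for both study arms during the post-treatment period".

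On size, the SAP states that "A total of 190 study participants were enrolled", and protocol section 8.9.1 that "Random assignment will be conducted using an allocation ratio of 2:1". The sample size was set for the FEV1 responder endpoint only (protocol section 20.3.1).

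**The concern.** Safety is a named endpoint, and the revised SAP makes it a comparison between arms. A Fisher p-value does not say how large an excess is or how large it could still be. The exact intervals in SAP VII describe each rate on its own. They do not give the precision of the difference.

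The gap matters most for the later period. Similar rates are anticipated there, and a p-value above 0.05 cannot support similarity, especially in a trial not sized for any safety comparison. An interval for the difference would show which excesses the data rule out.

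The omission is also uneven. For additional and purely informational variables, SAP IV.C describes the arms comparatively by mean change or difference in proportions. Adverse events get no such contrast.

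**Working it through.** **1. The plan's own figure.** Inputs from protocol section 20.3.1: 35% v 10% responders, two-sided alpha 0.05, 90% power, 2:1 allocation.

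- Pooled rate = (0.10 + 2 × 0.35)/3 = 0.2667.
- Control n without continuity correction = [1.960 × √(1.5 × 0.2667 × 0.7333) + 1.2816 × √(0.10 × 0.90 + 0.35 × 0.65/2)]² / 0.25² = (1.0615 + 0.5785)²/0.0625 = 43.03.
- With continuity correction: (43.03/4) × [1 + √(1 + 6/(2 × 43.03 × 0.25))]² = 48.9, so 49 control + 98 EBV = 147, as stated.
- 147/0.8 = 183.75, against 183 stated.

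The documents give no power figure for any safety comparison.

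**2. Arm sizes.** 190 × 2/3 = 126.7 and 190/3 = 63.3, taken as 127 EBV and 63 control. The documents do not state this split.

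**3. Power of Fisher's test.** All 128 × 64 possible tables were enumerated. Power is the sum of Bin(x; 127, pT) × Bin(y; 63, pC) over tables with two-sided p ≤ 0.05 and a higher observed rate with EBV. Alpha 0.05 is assumed.

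| Control rate | Power, 5-point excess | Power, 10-point excess | Excess needed for 80% power |
|---|---|---|---|
| 0% | 19% | 90% | 8.9 points |
| 1% | 20% | 76% | 10.6 |
| 3% | 18% | 60% | 13.0 |
| 5% | 15% | 50% | 14.6 |
| 10% | 12% | 37% | 17.5 |
| 20% | 9% | 27% | 20.4 |

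The smallest EBV counts that reach p ≤ 0.05 are 9/127 against 0/63 (7.1 points), 16/127 against 2/63 (9.4 points) and 28/127 against 6/63 (12.5 points).

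**4. What a non-significant result leaves open.** Miettinen-Nurminen 95% limits are the values Δ that solve (d − Δ)/√v(Δ) = ±1.96. Here d is the observed difference, v(Δ) = [p̃T(1 − p̃T)/127 + p̃C(1 − p̃C)/63] × 190/189, and p̃T, p̃C are the maximum likelihood rates under p̃T − p̃C = Δ.

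| EBV v control | Difference | Fisher p | 95% interval for the difference |
|---|---|---|---|
| 4/127 v 0/63 | +3.1 | 0.30 | −2.7 to +7.8 |
| 7/127 v 0/63 | +5.5 | 0.098 | −0.4 to +11.0 |
| 10/127 v 1/63 | +6.3 | 0.10 | −1.2 to +12.6 |
| 25/127 v 6/63 | +10.2 | 0.095 | −1.2 to +19.8 |

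**5. What the planned per-arm intervals show.** For 7/127 v 0/63 the exact intervals are 2.2% to 11.0% and 0% to 5.7%. They overlap, and overlap is easily taken for no difference. They do not show directly that an excess of about 11 points is still compatible with the data.

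**The case against.** Four stronger readings are tempting, and the documents do not support them.

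- **That the comparison rests on p-values with no intervals at all.** The sentence just before the Fisher sentence plans exact intervals on the rates, and the point difference follows by subtraction. The SAP change history says "Confidence intervals were removed from adverse event reporting", but section VII still has them and the current text governs. Only the estimate and interval for the contrast are missing.
- **That the plan would declare no difference when p exceeds 0.05.** No such rule exists, and study success rests on FEV1 alone. The misreading is a risk in reporting.
- **That real device harms will be missed.** This depends on their size and on the control rate. Power is 53% for 7% v 0% and 90% for 10% v 0%. It is about 100% for the anticipated one-in-five pneumothorax rate (protocol section 15.3.1) against an assumed control rate of 0%.
- **That protocol section 15.1 sets up an equivalence claim.** It states an expectation. Per-arm rates in the later period also bear on it.

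Other safeguards exist: SAP VIII for deaths, rehospitalization rates by arm, event adjudication and DSMB review. The choice of interval is partly preference. For 8/127 v 0/63 (p=0.054), Miettinen-Nurminen gives +0.4 to +12.0 and Newcombe −0.2 to +11.9, so no weight is put on whether the lower limit excludes zero. Nor does an interval make a small trial more powerful.

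These points narrow the concern but do not remove it. Per-arm intervals do not replace an interval for the difference, and the upper limits barely depend on the method: for 25/127 v 6/63, +19.8 against +19.4 by Newcombe.

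**Conclusion.** The point holds in this limited form: SAP VII provides per-arm rates, per-arm exact intervals and a Fisher p-value, but no between-arm risk difference with an interval. Power for a 5-point excess is about 9% to 20%. Depending on the control rate, a true excess of 8.9 to 20.4 points is needed for 80% power. Non-significant results can therefore sit alongside possible excesses of 12 to 20 points and may be misread as similar safety.

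This rests on a derived 127 v 63 split, an assumed two-sided alpha of 0.05, all randomised participants counted in each period, and illustrative event counts. It is a cheap and worthwhile improvement to the reporting of a named endpoint. It does not affect the primary analysis.

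**What to change.** In SAP VII, for each adverse event category and each serious event, in each of the two periods:

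- Report the between-arm risk difference with a 95% score interval (for example Miettinen-Nurminen) as the main comparison.
- Keep the per-arm exact intervals, and confirm that they stay in view of the change-history entry.
- Keep Fisher p-values as descriptive flags.
- State that non-significance is not evidence of similar risk, and that the section 15.1 expectation of similar long-term rates will be read from the interval.

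Deaths stay under the SAP VIII Kaplan-Meier, log-rank and Cox analyses.

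The cost is some SAP wording and one more table column. No new data are needed. Many of the intervals will be wide and will look less favourable than a column of non-significant p-values.
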